8.4.2.3.2 Blood PD (Serum)

A similar approach to Section 8.4.2.3.1 will be used, except that “Visit” is a three level term (DV1 24h Post Dose, DV8 Pre-Dose and DV8 24h Post Dose) and only the additional comparison involving DV8 is relevant. Baseline is still DV1 Pre-Dose.

8.4.2.3.3 Blood PBMC

NOT PART OF SAC DELIVERABLE: These samples will be stored and further processing would be subject to study outcome determined from the other endpoints (statistical analyses would be reported separately and methods documented in the corresponding write up / report). Possible processing would involve CHIP-cytometry with an interest in characterising differences in cell populations (e.g. B cells and T-cells) between the treatment arms after dosing with drug.

8.4.2.3.4 Blood sample for RNA analysis

Gene expression (Affy CHIP) data. Standard GSK processes for QC of each CHIP and the normalisation procedure will be employed (e.g. using Array Studio software).

The model to be fitted to each probeset will be a repeated measures model (this may be fitted in SAS PROC MIXED). It will be based on the appropriate “R” model (See Section 11.9.1) using (transformed) DV1 Pre-Dose as Baseline, Visits are DV8 and FUV2 with the following additional terms.

Fixed Categorical: Intercept

Fixed Continuous Covariates: Baseline*Visit

The repeated measures term is Visit (Subject = Subject), with an Unstructured variance covariance matrix common to each treatment arm (2x2).

Back transformed adjusted within visit Treatment comparisons (fold changes) and p-values (from a null hypothesis that the fold change=1) would be provided to the Computational Biology group within GSK for each probeset. That group will follow its processes (e.g. apply an appropriate false discovery rate correction (and possibly a threshold on the magnitude of fold change)) and place the resulting subset of genes into a pathway analysis. The Computational Biologist (or designate) would contribute directly to the corresponding CPSR sections with the interpretation of the pathway analysis outcome(s); and to describe any additional methodologies.

8.4.2.3.5 FeNO (Exhaled Nitric Oxide)

This section has been written assuming that FeNO response will require a log transformation. If it is not the case then appropriate modification should be made (e.g. comparisons expressed as differences rather than ratios (fold changes)).

Statistical Analysis of “Treatment induced changes” FeNO Samples

- Tables of descriptive summary statistics and Figures of type PD_F1 (but modified to use the PD_F3 axis layouts; i.e. one panel per subject with visit as the x-axis category and join the pre-dose values together for each subject across visits) and PD_F3.
- A Bayesian repeated measures mixed effect model, with non-informative priors for all model parameters, will be fitted to each of the post DV1 transformed responses collected from an individual subject (i.e. 7 data points per subject; the Pre-Dose values for DV2 to DV8 inclusive).
- Baseline: (Transformed) DV1 Pre-Dose
- The additional terms to include in the chosen “R” model (see Section 11.9.1) are:

Fixed Categorical: Intercept

Fixed Continuous Covariates: Baseline*Visit

The repeated measures term is Visit (Subject = Subject), with an Unstructured variance covariance matrix common to each treatment arm (7x7).

8.4.2.4 PGx Samples

These samples will be stored and further processing would be subject to study outcome determined from the other endpoints (statistical analyses would be reported separately and methods documented in the corresponding write up / report).

8.4.3 Multivariate / Composite endpoint analyses

Given the exploratory nature and timing in the overall clinical development program of this study, it is anticipated that further post-hoc analyses would be conducted on the data beyond those specified in this section. However, these would be data driven and difficult to pre-specify. Any post-hoc analyses would be labelled as such in their title, take the next available display number(s) and be described in the CPSR.

8.4.3.1 Correlation between Sputum and WBC cell differentials

Using the Sputum population scatterplots of BAC Sputum and WBC Differential cell results (both absolute counts and percentage variables) will be produced for each cell differential evaluated that is comparable over both sampling matrices. Simple linear regression lines may be overlaid onto the plot for i) each individual treatment arm and ii) all data combined (i.e. these would be simple regressions that do not account for the repeated measures on individuals when estimating the regression parameters and are intended to act as a rough indicator for how translatable conclusions drawn from analyses of WBC Differentials may be to the lung (BAC Sputum)). The plots will display all of the available data from all visits.

8.4.3.2 Defining responder / non-responder status for an individual subject using only their datapoints

For each subject the criteria in [Table 15](#) will be evaluated. If the endpoint relating to a question is missing then the subject's response will be set to missing and they would not contribute to the denominator when deriving any proportions.

Table 15 Criteria to be derived/applied at an individual subject level

ID	Area	Question(s)	Statistical Population	Endpoint(s)	Criteria / Responder algorithm (for non-missing endpoints)	Expected rate on Pbo Arm
A1	Target Engagement	Sustained activation of GSK2245035 target pathway?	Per Protocol	Within visit fold change in Nasal Lavage IP-10 (24h / Pre-Dose) at DV1 and DV8	Yes: Fold change ≥ 2 for BOTH DV1 and DV8 visits No: Any other outcome	<5% from 3x Previous studies (TL7114450, TL7116392, TL7116958)
B1 (FUV1) B2 (FUV2) B3 (FUV3)	Clinical BAC endpoint(s)	At least 20% attenuation of LAR Response c.f. SV?	Per Protocol	FUV1: WM and Min LAR FEV1 absolute change from saline FUV2: WM and Min LAR FEV1 absolute change from saline FUV3: WM and Min LAR FEV1 absolute change from saline	Derive Separately for each FU Visit Yes: $\geq 20\%$ Attenuation (c.f. SV) observed for either WM or Min LAR endpoint No: Any other outcome	~40% from 8x Historical GSK Allergen challenge studies (EL11002, HZA113126, INO102141, IPA101985, LPA111834, RES104385, RES114748 and SIG110762)
C1 (FUV1) C2 (FUV2) C3 (FUV3)	Clinical BAC endpoint(s)	At least 20% attenuation of EAR Response c.f. SV?	Sputum Producer	FUV1: WM and Min EAR FEV1 absolute change from saline FUV2: WM and Min EAR FEV1 absolute change from saline FUV3: WM and Min EAR FEV1 absolute change from saline	Derive Separately for each FU Visit Yes: $\geq 20\%$ Attenuation (c.f. SV) observed for either WM or Min EAR endpoint No: Any other outcome	~50% from 8x Historical GSK Allergen challenge studies
D1 (FUV1) D2 (FUV2) D3	Pre-BAC Endpoint(s)	Any Reduction in Pre-BAC Sputum EOS c.f. SV	Sputum Producer	Pre-BAC Sputum EOS (%) for FUV1, FUV2 and FUV3	Derive Separately for each FU Visit Yes: FU visit Sputum EOS % $<$ corresponding SV % No: Any other outcome	~50% (Assumption of no underlying change)

ID	Area	Question(s)	Statistical Population	Endpoint(s)	Criteria / Responder algorithm (for non-missing endpoints)	Expected rate on Pbo Arm
(FUV3)						
E1 (FUV1) E2 (FUV2) E3 (FUV3)	BAC Induced Changes in Endpoint(s)	Reduced Fold change in Sputum EOS (24h Post BAC/Pre-BAC) c.f. SV	Sputum Producer	Within Visit fold change in Sputum EOS (%) [24h Post BAC / Pre-BAC] at FUV1, FUV2 and FUV3	Derive Separately for each FU Visit Yes: FU visit Fold change < corresponding SV fold change No: Any other outcome	~50% (Assumption of no underlying change)
F1 (FUV1) F2 (FUV2) F3 (FUV3)	Pre-BAC Endpoint(s)	Any Reduction in Pre-BAC Blood EOS c.f. SV	Sputum Producer	Pre-BAC Blood EOS (%) for FUV1, FUV2 and FUV3	Derive Separately for each FU Visit Yes: FU visit Blood EOS % < corresponding SV % No: Any other outcome	~50% (Assumption of no underlying change)
G1 (FUV1) G2 (FUV2) G3 (FUV3)	BAC Induced Changes in Endpoint(s)	Reduced Fold change in Blood EOS (24h Post BAC/Pre-BAC) c.f. SV	Per Protocol	Within Visit fold change in Blood EOS (%) [24h Post BAC / Pre-BAC] at FUV1, FUV2 and FUV3	Derive Separately for each FU Visit Yes: FU visit Fold change < corresponding SV fold change No: Any other outcome	~50% (Assumption of no underlying change)
H1 (FUV1) H2 (FUV2)	Pre-NAC Endpoint(s)	Any Reduction in Pre-NAC Nasal Lavage IL-5 c.f. SV	Per Protocol	Pre-NAC Nasal Lavage IL-5 for FUV1 and FUV2	Derive Separately for each FU Visit Yes: FU visit NL IL-5 < corresponding SV value No: Any other outcome	~50% (Assumption of no underlying change)
I1 (FUV1) I2 (FUV2)	NAC Induced Changes in Endpoint(s)	Reduced Fold change in Nasal Lavage IL-5 (6h Post NAC/Pre-NAC)	Per Protocol	Within visit fold change in Nasal Lavage IL-5 [6h Post NAC / Pre-NAC] at FUV1 and FUV2	Derive Separately for each FU Visit Yes: FU visit Fold change < corresponding SV fold change No: Any other outcome	~50% (Assumption of no underlying change)

ID	Area	Question(s)	Statistical Population	Endpoint(s)	Criteria / Responder algorithm (for non-missing endpoints)	Expected rate on Pbo Arm
		c.f. SV				
J1 (FUV1) J2 (FUV2)	Pre-NAC Endpoint(s)	Any Reduction in Pre-NAC Nasal Lavage ECP c.f. SV	Per Protocol	Pre-NAC Nasal Lavage ECP for FUV1 and FUV2	Derive Separately for each FU Visit Yes: FU visit NL ECP < corresponding SV value No: Any other outcome	~50% (Assumption of no underlying change)
K1 (FUV1) K2 (FUV2)	NAC Induced Changes in Endpoint(s)	Reduced Fold change in Nasal Lavage ECP (6h Post NAC/Pre-NAC) c.f. SV	Per Protocol	Within visit fold change in Nasal Lavage ECP [6h Post NAC / Pre-NAC] at FUV1 and FUV2	Derive Separately for each FU Visit Yes: FU visit Fold change < corresponding SV fold change No: Any other outcome	~50% (Assumption of no underlying change)
L1 (FUV1) L2 (FUV2) *	Pre-NAC Endpoint(s)	Any Reduction in Pre-NAC Nasal Filter Eotaxin c.f. SV	Per Protocol	Pre-NAC Nasal Filter ECP for FUV1 and FUV2	Derive Separately for each FU Visit Yes: FU visit NF ECP < corresponding SV value No: Any other outcome	~50% (Assumption of no underlying change)
M1 (FUV1) M2 (FUV2) *	NAC Induced Changes in Endpoint(s)	Reduced Fold change in Nasal Filter Eotaxin (6h Post NAC/Pre-NAC) c.f. SV	Per Protocol	Within visit fold change in Nasal Filter Eotaxin [6h Post NAC / Pre-NAC] at FUV1 and FUV2	Derive Separately for each FU Visit Yes: FU visit Fold change < corresponding SV fold change No: Any other outcome	~50% (Assumption of no underlying change)

* = Only included if the Nasal Filter Eotaxin biomarker was processed / evaluated

A subject level listing will be produced to display the results of each question in [Table 15](#) (and any additional post-hoc data driven questions). The proportion of individuals in the Yes category will be derived for each treatment arm and question, using both the main and alternative set of treatment descriptors (i.e. derive a separate proportion for each descriptor). These proportions will be listed and also displayed on starcharts (sometimes called radar plots), with a separate spoke per question and a separate chart per visit, with the treatment profiles overlaid on the individual panels (answers to questions which do not naturally have a visit structure will be duplicated across each visit/starchart). Aim to get all visits on the same page and align question B to the top spoke and present the questions in the following clockwise order: B, C, D, F, H, E, G, I, J, K, L, M and A. If possible use the same axis scale for each spoke, but question A may produce a wide range of proportions and therefore it is acceptable to present some questions on a different spoke axis scale to aid interpretation of any questions where smaller treatment differences are observed. To allow for (data driven) modifications to the number and/or ordering of the question a listing linking the abbreviated IDs to the actual questions/criteria will also be produced and any new questions/criteria not in [Table 15](#) should be appropriately identified (e.g. using a lower case “p” as a suffix to the new question ID).

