8 SECONDARY STATISTICAL ANALYSES

8.1 Efficacy Analyses

8.1.1 Overview of Planned Efficacy Analyses

The secondary (and exploratory) efficacy analyses presented in this section will be based on the PP population, unless otherwise specified (the exception being the repeated measures version of the primary efficacy endpoint analysis which will also be run using the mITT population (conditional on the PP and mITT populations differing)). Note: For ease of review the exploratory repeated measures analyses for LAR and EAR endpoints are also described in this section.

Table 6 provides an overview of the planned efficacy analyses, with further details of data displays being presented in [Appendix 13: List of Data Displays](#).

Table 6 Overview of Planned Efficacy Analyses

Endpoint	Absolute							
	Stats Analysis			Summary		Individual		
	T	F	L	T	F	F	L	
LAR								
Min and WM FEV ₁ absolute change from saline from FUV1, FUV2 and FUV3 visits (Repeated measures)	Y	Y	Y	Y	Y	Y	Y	Y
EAR								
Min and WM FEV ₁ absolute change from saline at Week 9 (FUV1)	Y	Y	Y	Y	Y	Y	Y	Y
Min and WM FEV ₁ absolute change from saline from FUV1, FUV2 and FUV3 visits (Repeated measures)	Y	Y	Y	Y	Y	Y	Y	Y

NOTES :

- T = Table, F = Figure, L = Listing, Y = Yes display generated.
- Stats Analysis = Represents TFL related to any formal statistical analyses (i.e. modelling) conducted.
- Summary = Represents TFL related to any summaries (i.e. descriptive statistics) of the observed raw data.
- Individual = Represents FL related to any displays of individual subject observed raw data.

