8.4.2.1.2 Blood WBC and Differential Cell Counts

As with sputum, the emphasis is on the Eosinophils. These are expected to increase upon BAC challenge (i.e. increases on Placebo c.f. pre-BAC values), and GSK2245035 should “blunt” this increase (*a priori* it is not certain if the treatment effect is sufficiently strong that it causes decreases, rather than a reduced level of increase c.f. Placebo).

The analysis approach is similar to Section [8.4.2.1.1](#); except that the All Subjects population is to be used and the list of differential cell types from the Blood Haematology samples is different (no Macrophages, BEC or Total Non-Squamous Cells but Monocytes and Basophils are expected). Also and if present in the source data only the total Neutrophils should be descriptively summarised/analysed (not Segs and Bands). Total WBC should also be modelled.

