8.4.2.2.1 Nasal Lavage Fluid & Nasal Lavage Filters

Nasal Lavage Fluid samples are expected to provide the Mast Cell Mediator results (plus ECP and allergen specific IgA). Nasal Filters are expected to provide the Inflammatory mediators (chemokines and cytokines).

Statistical Analysis of “Background” Samples

- Additional Figures of type PD_F3
- Separate Bayesian repeated measures mixed effect models (per analyte), with non-informative priors for all model parameters, will be fitted to each transformed response over the planned post Screening time points (FUV1 and FUV2).
- Baseline: (Transformed) SV Background
- The additional terms to include in the chosen “R” model (see Section 11.9.1) are:

Fixed Categorical: Intercept

Fixed Continuous Covariates: Baseline*Visit

The repeated measures term is Visit (Subject = Subject), with an Unstructured variance covariance matrix common to each treatment arm (2x2).

Statistical Analysis of “Direct NAC effect” Samples

- Additional Figures of type PD_F2 and PD_F4
- Separate Bayesian repeated measures mixed effect models (per analyte), with non-informative priors for all model parameters, will be fitted to each of the transformed responses collected from an individual subject (i.e. 6 data points per subject; the combinations of Visit and Sample times SV Pre-NAC, SV Post NAC, FUV1 Pre-NAC, FUV1 Post NAC, FUV2 Pre-NAC and FUV2 Post NAC; where Post-NAC is either 5m or 6h depending whether the biomarker is a mast cell mediator (5m) or inflammatory (6h)).
- For the purposes of assessing models R1 to R3 (see Section 11.9.1) consider “Visit” in those models to be a six level term covering the data recorded per subject with these additional terms:

Fixed Categorical: Intercept

The repeated measures term is Visit (Subject = Subject), with an Unstructured variance covariance matrix common to each treatment arm (6x6).

- In this model parameterization the usual “Baseline” timepoints (Pre-NACs) are modeled as response variables and not covariates. Therefore posterior distributions for the quantities of interest; namely treatment effect on “within visit fold changes (Post/Pre) adjusted for the screening visit and placebo fold changes”; use fold changes representing the mean predicted response at the timepoint (and not the average of the individual subjects fold changes).

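### SAP Table 15 restricts EAR and pre-challenge blood eosinophils to sputum producers without a reason, and names the wrong analyte or sample in three nasal rows

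*SAP*

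**What the plan says.** Table 15 gives each question a population, an endpoint and a yes/no algorithm.

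- **Row C (C1-C3):** "At least 20% attenuation of EAR Response c.f. SV", Sputum Producer population. Its LAR counterpart, row B, is Per Protocol.
- **Row F (F1-F3):** "Any Reduction in Pre-BAC Blood EOS c.f. SV", Sputum Producer population. The other blood eosinophil question, row G, "Reduced Fold change in Blood EOS (24h Post BAC/Pre-BAC) c.f. SV", is Per Protocol.
- **Rows H and I:** row H asks "Any Reduction in Pre-NAC Nasal Lavage IL-5 c.f. SV"; row I asks about the 6-hour fold change in the same lavage analyte.
- **Row L:** the question concerns nasal filter Eotaxin, but the endpoint is "Pre-NAC Nasal Filter ECP for FUV1 and FUV2" and the algorithm also scores ECP. A footnote keeps rows L and M only if filter Eotaxin was assayed.

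Elsewhere the SAP sets different rules. On EAR, section 8.1.1 states: "The secondary (and exploratory) efficacy analyses presented in this section will be based on the PP population". On blood differentials, section 8.4.2.1.2 follows the sputum approach "except that the All Subjects population is to be used". On nasal samples, section 8.4.2.2.1 states: "Nasal Filters are expected to provide the Inflammatory mediators (chemokines and cytokines"; it gives lavage fluid the mast cell mediators, ECP and allergen-specific IgA. Table 12 agrees: IL-5 is an expected filter analyte, Eotaxin a conditional one, and ECP is not on the filter panel.

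**The concern.** A responder table is programmed row by row, so a wrong population or analyte in a row passes straight into the output. Two kinds of fault are present.

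Rows C and F use a population defined by a sample that their endpoints do not use. In section 4, Sputum Producers are a subset of All Subjects with a viable screening sputum sample, not a subset of Per Protocol. The assignment therefore changes the patients in both directions: Per Protocol subjects without sputum leave, and sputum producers excluded from Per Protocol can enter. The EAR rate is then not on the same footing as the LAR rate in row B, nor clearly comparable with the 50% placebo rate quoted for row C, which comes from eight historical studies with no stated sputum restriction.

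Rows H, I and L name an analyte in a sample where the SAP does not plan to measure it. At stake is whether the starcharts, which put these proportions on one display, preferably on a common axis scale, show what their labels say.

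**Working it through.** The documents give no figure to reproduce here. The check compares Table 15 with the rest of the SAP, counts the affected items, and gives an illustrative precision calculation.

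**1. Population check.**

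| Row | Needs sputum? | Table 15 population | Partner row | Rule elsewhere in the SAP |
|---|---|---|---|---|
| C (EAR) | No | Sputum Producer | B (LAR): Per Protocol | Per Protocol (8.1.1) |
| F (pre-BAC blood eosinophils) | No | Sputum Producer | G (blood eosinophil fold change): Per Protocol | All Subjects (8.4.2.1.2) |
| D, E (sputum eosinophils) | Yes | Sputum Producer | not applicable | Sputum Producer (8.4.2.1.1) |

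D and E are consistent; C and F are not.

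**2. Analyte check.**

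| Row | Question | Endpoint scored | Planned nasal sample for that analyte |
|---|---|---|---|
| H, I | Lavage IL-5 | Lavage IL-5 | Filter |
| J, K | Lavage ECP | Lavage ECP | Lavage (agrees) |
| L | Filter Eotaxin | Filter ECP | ECP: lavage; Eotaxin: filter, conditional |
| M | Filter Eotaxin | Filter Eotaxin | Filter, conditional (agrees) |

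Section 8.4.3.2 sets a subject's answer to missing, and removes the subject from the denominator, when the endpoint is missing. Followed literally, H, I and L give 0/0. If a programmer put lavage ECP into row L, it would simply repeat row J.

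**3. Count.** Items by visit: A has 1; B to G have 3 each (18); H to M have 2 each (12). The total is 1 + 18 + 12 = 31.

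- Population mismatch: C 3 + F 3 = 6.
- Analyte or sample mismatch: H 2 + I 2 + L 2 = 6.
- Together 12 of 31, or 5 of the 13 spokes on the first follow-up chart (C, F, H, I, L). These counts include the conditional rows L and M.

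**4. Precision for C and F.** The documents do not give the proportion of subjects who produce sputum. Assume 50-70% of the 20 completers per arm targeted in protocol section 4.3, so n is 10 to 14. For a difference between two proportions near 50%, SE = sqrt(2 × 0.25 / n):

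- n = 20: sqrt(0.5/20) = 0.158
- n = 14: sqrt(0.5/14) = 0.189
- n = 10: sqrt(0.5/10) = 0.224

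**5. Possible shift in a rate.** If a fraction f produce sputum and their EAR responder rate differs from that of non-producers by d, the producers' rate differs from the all-subject rate by (1 − f) × d. With d assumed to be 0.10 to 0.20, the shift is 0.03 to 0.06 at f = 0.7 and 0.05 to 0.10 at f = 0.5.

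**The case against.** Several points on the other side carry weight.

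- **Mixed populations are foreseen.** The programming note to Listing 98 says questions may use different populations, and D and E must stay with sputum producers. Missing endpoints also leave each denominator separately. The spokes will therefore differ in patients after any edit, and the treatment comparison within a spoke remains valid for C and F. This stands, but it gives no reason for C or F.
- **Row F might be meant to mirror sputum eosinophils.** Section 8.4.3.1 compares sputum and blood cells in the sputum population, and the starchart places D beside F. The rationale is plausible but unstated, and row G, the blood counterpart of sputum row E, is Per Protocol. No such rationale suggests itself for C.
- **The lavage label is sometimes an umbrella.** The heading of 8.4.2.2.1 and the display titles in 11.13.11 and 11.13.12 use it for fluid and filter together. IL-5 is planned in only one nasal sample, and section 8.4.2 says the analyte list is not final. The file-naming example in 11.4.3 also cites nasal lavage IL-5. Against this, Table 15 itself separates lavage from filter, and that example uses the code for lavage fluid, not the one for filters.
- **Row L's intent is recoverable** from its question, its footnote and row M. That is true, but the endpoint and algorithm are what gets programmed.

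A reader might infer that blood eosinophils are scored only in sputum producers. They are not: row G is Per Protocol, and section 8.4.2.1.2 models blood differentials in All Subjects. A reader might also infer that the C and F rates are wrong. Each would be a correct proportion for the population named; the fault is that the population is unexplained and does not match that of the partner row.

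**Conclusion.** The inconsistencies are real and minor. Rows C and F carry an unexplained population that conflicts with their partner rows and with the SAP's other rules for the same data. Row L contradicts itself. Rows H and I name a sample in which IL-5 is not planned.

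One might go further and call H and I entirely missing. That holds only on the literal reading; given the umbrella use of the lavage label, the documents support a conflict to be resolved, not certain emptiness. The case for L is firmer, because ECP is not on the filter panel under either reading.

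The size is 12 of 31 items. The rise in standard error for C and F, from about 0.16 to 0.19-0.22, rests on an assumed 50-70% sputum yield and on 20 completers per arm. That number is a target and not the Per Protocol count. No test or interval is planned for these proportions, so the standard errors only indicate how much noisier the plotted rates would be. The shift of 3 to 10 percentage points rests on a further assumed gap between producers and non-producers.

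The effect is confined to the exploratory responder listings (97-99) and the starcharts (Figure 5.69). The primary LAR and secondary EAR models are unaffected.

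**What to change.** Before database freeze:

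1. Set rows C and F to Per Protocol. If Sputum Producers was intended for either, state why.
2. Change row L's endpoint and algorithm to nasal filter Eotaxin, as in row M. The row stays conditional on Eotaxin being assayed.
3. Name nasal filter IL-5 in the question, endpoint and algorithm of rows H and I, and bring the file-naming example in 11.4.3 into line. If IL-5 in lavage fluid is really wanted, add it to Table 12 and section 8.4.2.2.1 instead.

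The cost is edits to five table rows and one example, with no change to data collection or to any model. Timing matters more than effort. The SAP synopsis commits to settling final-analysis decisions before the freeze, and the headline snapshot in section 3.2 is unblinded and precedes it. A dated correction made before that snapshot could not be taken for a data-driven choice of population or analyte.

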Nasal lavage			X	Collect nasal lavage to provide a background sample. Repeat nasal lavage pre-NAC, then again 5 minutes and at least 6 hours post-NAC.
Nasal filter collection			X	Collect nasal filter sample to provide a background pre-wash sample, after nasal wash repeat nasal filter sampling pre-NAC, then again 5 minutes and at least 6 hours post-NAC.
NAC			X	Commence after the 24-hour BAC sputum and blood biomarker samples have been taken. Only to be done once subjects have completed a successful BAC.
ID challenge			X	ID challenge to be administered after NAC. Measurements to be made 15 minutes and 6 hours post ID challenge.
Nasal scrape			X	Nasal mucosa sample to be collected at least 6 hours post-NAC.

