Blood Samples for PBMC preparations	BAC induced allergic inflammatory cell populations	Blood PBMC	n/a	ZKW	Conditional on other study endpoints showing positive signals Reported outside of CPSR as data generation may take a long time	To be defined, analysis of BAC induced allergic inflammatory populations in PBMC.	To be defined, reduction in BAC induced allergic inflammatory populations in PBMC.

T&E procedure	"Informal" description / rationale for samples	Matrix	Functional Categories	Vendor (Δ)	Analyte(s)	Comments	
						Anticipated Placebo profile	Characteristics of Successful drug effect
Nasal lavage	Changes in time (Background timepoint) Direct NAC effects	Lavage	Immuno-globulins Eosinophil mediators	GSK (Stevenage)	Background Pre-NAC & 6h Post NAC samples only (Allergens are "Birch", "House Dust Mite", "Cat" and "Grass" – Expecting one result per subject using the allergen they were challenged with – but re-label to "Allergen Specific IgA" for displays; only German sites expected to provide Birch Allergen data) ECP, Allergen Specific IgA	NAC should increase inflammatory mediators	Treatment related changes compared to screening of either background levels or the NAC induced increase at 6 hrs (6h/Pre-NAC ratio) Eosinophil mediators should go down or not increase on NAC if drug is working & IgA should increase
			Mast Cell mediators	GSK (Stevenage)	Pre-NAC & 5m Post NAC samples only Histamine Tryptase Conditional:	Mast cell mediators should increase in 5 min post NAC sample	Reduction in the NAC (5 min/pre-NAC ratio) induced response after treatment

T&E procedure	"Informal" description / rationale for samples	Matrix	Functional Categories	Vendor (Δ)	Analyte(s)	Comments	
						Anticipated Placebo profile	Characteristics of Successful drug effect
					Prostaglandin D2		compared to the SV
	TLR7 Induced changes (confirm target engagement)	Lavage	"TLR7" Target engagement	GSK (Stevenage)	IP-10	Within visit ratio (24h / Pre-dose) should be approximately one	Increase in within visit fold changes to confirm target engagement. Investigate whether the magnitude of fold changes at DV4 and DV8 are similar

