8.4.2.2 Biomarkers Supporting the NAC related exploratory objective(s)

The Background samples should be analysed separately from the others as their intent is to capture changes in condition over the season (longer term changes).

The Pre-NAC, 5min and 6 hours are designed to measure the direct (within day) impact of the NAC procedure. The pre-wash (applied as part of the process to obtain the background sample) should also make the pre-NAC values more consistent (essentially zero) and should ensure that subjects should begin from a similar nasal condition (i.e. with a clean nose). Thus challenge related changes should be more consistent as mediators induced by the challenge should be the dominant items detected.

However, although all post NAC samples may be collected, not all of the biomarker types will be evaluated in the first instance. Pre-NAC samples will be evaluated for all biomarker types (mast cell mediators and inflammatory mediators). Mast cell mediators will also be evaluated from the 5min sample and Inflammatory mediators will be also be evaluated for the 6h sample.

Whilst the statistical analysis may split the data initial summaries will be produced using the complete dataset (i.e. a “PD_F1” format Figure and summarised in descriptive tables).

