11.4.2.3 Imputation for Values Below and Above Limit of Quantification

PD responses which are below the assay's respective lower limit of quantification (LLQ) will be imputed using half of the LLQ value.

PD responses which are above the assay's respective upper limit of quantification (ULQ) will be imputed using the ULQ value.

In the event that multiple LLQ/ULQ values are present the minimum for that analyte (for LLQ) and maximum for that analyte (ULQ) should be used in the imputations. If any LLQ values are zero then a suitable small constant may be used in place, to allow the data to be log transformed (for example half of the smallest observed non-zero value).

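### SAP Table 15 scores nasal responders on the post-wash Pre-NAC sample rather than the Background sample, and its 50% placebo rate ignores ties below the LLQ

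*SAP*

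**What the plan says.** **Sampling order.** At each visit with a nasal allergen challenge (NAC), a background sample is collected, the nose is washed, and the Pre-NAC sample follows. For filters, the Protocol's Time and Events Table (7.1.1) reads "after nasal wash repeat nasal filter sampling pre-NAC".

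**Role of each sample.** SAP 8.4.2.2 says of the Background samples that "their intent is to capture changes in condition over the season", and that the wash "should also make the pre-NAC values more consistent (essentially zero"). SAP 8.4.2.2.1 models longer-term change on Background samples, with screening Background as baseline.

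**Definition of success.** For lavage, Table 12 (SAP 8.4.1) lists "Treatment related changes compared to screening of either background levels or the NAC induced increase at 6 hrs". The nasal filter row follows the same pattern. Neither names the Pre-NAC level alone.

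**Responder rule.** Table 15 asks "Any Reduction in Pre-NAC Nasal Lavage ECP c.f. SV" (J) and "Any Reduction in Pre-NAC Nasal Lavage IL-5 c.f. SV" (H). L has the same form for nasal filter eotaxin. The rule for J is "Yes: FU visit NL ECP < corresponding SV value No: Any other outcome". The expected placebo rate is given as about 50%, on the assumption of no underlying change.

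**Values below the LLQ.** Under SAP 11.4.2.3 these "will be imputed using half of the LLQ value". Where an analyte has several LLQs the smallest is used, and SAP 8.4.2 makes imputed values the default.

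**The concern.** Two things do not fit together.

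First, Table 15 looks for a lasting reduction in the sample from which the wash is meant to have removed the pre-existing mediator. The SAP assigns that question to another sample, so the mismatch exists whatever the assay limit turns out to be.

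Second, if the wash works as expected, some subjects will be below the LLQ at both screening and follow-up. Both values then equal the same half-LLQ constant, the strict inequality fails, and the subject scores No. The printed 50% makes no allowance for this.

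At stake is how the responder listings and starcharts read. A spoke for J could sit well below its printed reference, with the arms close together, because of censoring rather than absence of a drug effect.

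**Working it through.** **Inputs from the documents:** strict inequality, ties scored No, placebo rate about 50% (Table 15); one half-LLQ constant per analyte (SAP 11.4.2.3).

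**Input not in the documents:** q, the share of Pre-NAC values below the LLQ. A range is shown, with the same q at screening and follow-up when there is no drug effect.

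**1. The plan's figure.** With no underlying change, a fall and a rise are equally likely. If t is the probability of a tie, P(Yes) = (1 − t)/2. With t = 0 this is 0.50, so the stated rate is reproduced, but only without ties.

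**2. With ties.** A tie occurs when both visits are below the LLQ. If visits are independent, t = q²; if perfectly correlated, t = q. For non-negative correlation the placebo rate therefore lies between (1 − q)/2 and (1 − q²)/2. At q = 0.5 that is (1 − 0.5)/2 = 25% to (1 − 0.25)/2 = 37.5%.

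**3. Ceiling.** A screening value at half the LLQ cannot be undercut. In either arm P(Yes) is at most 1 − q, with q taken at screening.

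| q | Placebo, perfectly correlated | Placebo, independent | Ceiling, either arm |
|---|---|---|---|
| 0 | 50% | 50% | 100% |
| 0.25 | 37.5% | 46.9% | 75% |
| 0.5 | 25% | 37.5% | 50% |
| 0.75 | 12.5% | 21.9% | 25% |
| 0.9 | 5% | 9.5% | 10% |

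**4. Contrast between arms.** This step needs further assumptions: bivariate normal values on the log scale and a true 1 SD drop on active. It was simulated with 2,000,000 pairs per setting.

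| q | Placebo Yes (corr. 0.5) | Active Yes (corr. 0.5) | Difference, points (corr. 0.5) | Difference (corr. 0) | Difference (corr. 0.8) |
|---|---|---|---|---|---|
| 0 | 50.0% | 84.1% | 34.1 | 25.9 | 44.3 |
| 0.25 | 44.0% | 67.7% | 23.7 | 18.8 | 30.5 |
| 0.5 | 33.3% | 46.9% | 13.6 | 9.6 | 18.5 |
| 0.75 | 19.0% | 24.2% | 5.2 | 2.6 | 8.1 |
| 0.9 | 8.4% | 9.8% | 1.4 | 0.5 | 2.7 |

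The contrast is lost gradually and vanishes only as q approaches 1.

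**5. Which criteria this covers.** J fits directly, because Table 12 plans ECP in lavage at the Background, Pre-NAC and 6-hour samples. H names nasal lavage IL-5, but Table 12 and SAP 8.4.2.2.1 plan IL-5 from filters. L asks about eotaxin, while its endpoint and rule name nasal filter ECP, which Table 12 does not list; L also applies only if eotaxin is assayed. Read literally, H and L have no planned data. SAP 8.4.3.2 sets such responses to missing and drops them from the denominator, so they would not score No.

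**The case against.** The strongest reply is that the size of the problem is unknown. SAP 8.4.2.2 states what the wash should achieve; it reports no measured result, and neither document gives a nasal LLQ or a share of values below it. With q at 0.25 or less, criterion J would still separate the arms under the assumptions above. This stands, and it limits what can be claimed about size. It does not remove the conflict over which sample to score.

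A second reply is that little is lost. The Background samples have their own repeated-measures models for each analyte, the listings show original and imputed values, and the subject plots draw LLQ lines where relevant, so heavy censoring would be visible. The starcharts overlay the two arms, so the natural comparison is arm against arm rather than arm against 50%. SAP 8.4.3.2 also allows the questions to be changed once data are seen. All of this is correct and keeps the point minor. A question added later would, however, carry the suffix that marks it as not pre-specified.

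A reader might go further and infer that H, J and L will return No for most subjects in both arms and cannot show a drug effect. The documents do not support that. The ceiling forces a majority of No only if q exceeds 0.5, the contrast disappears only near q = 1, and H and L as written would be missing rather than No. That a low rate would be misread as worsening is also speculation.

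**Conclusion.** The concern holds in limited form. Criterion J, and H and L once their analyte and matrix are corrected, score the wrong sample by the SAP's own account of what each sample is for. That conclusion needs no assumption about the assay.

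The 50% placebo rate is right only with few ties. How far it falls depends on q, which the documents do not give, and on the correlation between visits; the ranges above assume equal q at both visits and non-negative correlation. The loss of contrast between arms additionally rests on the assumed normal model and 1 SD effect.

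The consequence is confined to exploratory, descriptive proportions with no test or decision rule attached. The primary analysis and the Background repeated-measures models are unaffected. Severity: minor.

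**What to change.** In Table 15:

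- **J1/J2:** score follow-up Background against screening Background nasal lavage ECP.
- **H1/H2:** score Background nasal filter IL-5, and reconcile the matrix in I1/I2, which also names lavage IL-5.
- **L1/L2:** score Background nasal filter eotaxin, if assayed, and replace ECP in the endpoint and rule.
- **I, K and M:** keep the ratio of 6-hour to Pre-NAC values.
- **Ties:** report by arm the number of pairs with both values below the LLQ. Either show them as a separate category or leave them out of the comparison with 50%. Leaving them out restores the benchmark under no change, since [(1 − t)/2]/(1 − t) = 0.5. State that this departs from the default use of imputed values and that exclusions may differ between arms.

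The cost is SAP wording and a small programming change. Background samples are already collected, and Table 12 already lists them for lavage ECP and filter IL-5, and conditionally for filter eotaxin. Making the change before database freeze keeps the corrected questions pre-specified.
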